#### PROPOSED RESEARCH

- The IRB will not accept grant applications and/or sponsor's protocols in lieu of the items as outlined below.
- Do not separate responses from items. Instead, insert your response to each item below the item, keeping the information in the order of this form.
- Number each page of the Human Subjects Protocol (i.e., Page X of Y).

#### 13. Purpose—in nontechnical, lay language

Ushicle identifiers and serial numbers

Summarize the purpose and objectives of this protocol, including any related projects, in one short paragraph.

Obstructive sleep apnea (OSA) affects millions of people in the U.S., and currently, there is not a well-established, general anesthetic technique that clearly decreases the risk of postoperative respiratory complications in these patients. If OSA patients in our study group have significantly decreased postoperative opioid requirements and improved recovery profiles in the PACU, our protocol could have significant implications in defining future standardized general anesthesia recommendations for patients with this disease. Ultimately, the aim of this study is to substantially reduce overall postoperative morbidity and mortality associated with obstructive sleep apnea. The objective of this study is to compare the postoperative recovery profile of OSA patients receiving standard Sevoflurane inhaled anesthesia with normal saline infusion versus Sevoflurane combined with a low-dose ketamine infusion. We hypothesize that the group of obstructive sleep apnea patients that receive low-dose intraoperative ketamine will report lower pain scores, require less supplemental intravenous Morphine, and have less frequent side effects and desaturation episodes post-operatively than the group receiving saline.

#### 14. Background—in nontechnical, lay language

Summarize in 2-3 paragraphs past experimental and/or clinical findings leading to the formulation of this study. Include any relevant past or current research by the Principal Investigator. For drug and device studies summarize the previous results (i.e., Phase I/II or III studies).

Obstructive sleep apnea (OSA) has been estimated to affect between 2 and 4% of the U.S. population. It is a serious, life-threatening condition associated with obesity, hypertension, congestive heart failure, pulmonary hypertension, coronary artery disease, and cardiac arrhythmias and has an 8 year mortality rate of nearly 40%. Following general anesthesia, patients with OSA have been noted to have a significantly increased risk of respiratory complications, morbidity and mortality. This may be due to residual effects of inhaled anesthetics which can decrease upper pharyngeal muscle tone leading to airway compromise in OSA patients. Also, OSA patients are exquisitely sensitive to the ventilatory depressant effects of postoperative opioids, causing decreased responsiveness to hypercarbia and episodic arterial hypoxemia. Currently, there is not a well-established, general anesthetic technique that will decrease the risk of complications in OSA patients.

Obese patients are known to have a delayed emergence from anesthesia due to volatile gases' high affinity for adipose tissue. Also, adipose tissue serves as a depot for anesthetic gases during prolonged exposure. In addition, many obese patients presenting for surgery meet clinical screening criteria for obstructive sleep apnea. Surgical patients with obstructive sleep apnea patients are known to be very sensitive to the respiratory depressant effects of intravenous opioids in the postoperative period. When possible, opioids should be avoided in favor of nonsedating agents such as acetaminophen, ketorolac or even regional anesthesia when possible. Unfortunately, after major surgery, most patients will still require IV opioids titrated to effect in order to adequately control their pain.

Ketamine is a dissociative anesthetic agent that provides profound analgesia without depressing the respiratory system. Ketamine is extensively metabolized by hepatic p-450 enzymes to a weak, water-soluble compound that is excreted by the kidneys and has a short context-sensitive half-time (time for plasma level to drop by 50%) even during prolonged infusions. Multiple studies have demonstrated that intraoperative, subanesthetic dosing of ketamine can significantly reduce postoperative opioid requirements following major surgery. This low-dose of ketamine was also shown to decrease the incidence of postoperative nausea and vomiting and was not associated with an increase adverse psychotropic effects. None of these studies targeted obstructive sleep apnea patients to determine whether these opioid-sparing effects persist and could mitigate the postop respiratory compromise or improve their overall recovery profile.

#### 15. Participants (Screening and Selection)

- a. How many participants are to be enrolled at UAB?  $\underline{150}$  If multi-center study, total number at all centers:  $\underline{N/A}$
- **b.** Describe the characteristics of anticipated or planned participants.

Sex: Male or Female

Race/Ethnicity: All representative of patients undergoing general ENT or Orthopedic surgery; Expand the patient population to include all patients undergoing surgery requiring to general anesthesia due to the limited amount of patients that are able to be recruited.

Age: 18-100

Classification of 1-3 and who are morbidly obese patients with obstructive sleep apnea scheduled general ENT or Orthopedic surgery. ASA Classification of 1 = A normal healthy patient, ASA Classification of 2 = A patient with mild systemic disease (examples: current smoker, social alcohol drinker), ASA Classification of 3 = A patient with significant systemic disease (examples: Poorly controlled diabetes or hypertension), and ASA Classification of 4 = A patient with severe systemic disease that is a constant threat to life (examples: MI, CVA, TIA, or CAD/stents, ongoing

cardiac ischemia or severe valve dysfunction, severe reduction of ejection fraction, sepsis, DIC, ARD or ESRD not undergoing regularly scheduled dialysis).

Note. If data from prior studies indicate differences between the genders or among racial/ethnic groups in the proposed research or if there are no data to support or to negate such differences, Phase 3 clinical trials will be required to include sufficient and appropriate entry of gender and racial/ethnic subgroups so that trends detected in the affected subgroups can be analyzed. If ethnic, racial, and gender estimates are not included in the protocol, a clear rationale must be provided for exclusion of this information. If prior evidence indicates that the results will not show gender or racial differences, researchers are not required to use gender or race/ethnicity as selection criteria for study participants. They are, however, encouraged to include these groups. See Section II. Policy of the NIH POLICY AND GUIDELINES ON THE INCLUSION OF WOMEN AND MINORITIES AS SUBJECTS IN CLINICAL RESEARCH – Amended, October, 2001) for further details.

C. From what population(s) will the participants be derived?
The study population will be derived from those patients who are morbidly obese scheduled to undergo general ENT and orthopedic surgery.
Describe your ability to obtain access to the proposed population that will allow recruitment of the necessary number of participants:
All patients scheduled for the above surgical procedure will be seen preoperatively in the PAC at TKC and Highlands. The opportunity to participate will be offered at such time.

Describe the inclusion/exclusion criteria:

Inclusion criteria: aged 19-100, scheduled to undergo general ENT or Orthopedic Surgery.

Patients should have a diagnosis of obstructive sleep apnea as confirmed by sleep study or deemed high risked for obstructive sleep apnea by clinical predictors (greaterthan 4 clinical predictors of obstructive sleep apnea as described by STOP BANG).

Exclusion criteria: positive pregnancy test, ASA> III, history of alcohol or narcotic abuse in last 90 days, significant cardiovascular or respiratory disease (baseline oxygen saturation below 92%), significant psychiatric or neurologic disease, history of significant hepatic or renal disease (baseline creatinine>1.5), history of allergy or contraindication to anesthetic agents or ketamine including patients with increased ICP, increased IOP, severe arrhythmias, history of delirium, hallucinations, or psychosis, or history of uncontrolled seizures, or potential risk for malignant hyperthermia (family history), history of difficult intubation that would preclude standard induction of anesthesia, prisoners, persons who are mentally impaired, and non-English speakers.

- **d.** If participants will comprise more than one group or stratification, describe each group (e.g., treatment/intervention, placebo, controls, sham treatment) **and** provide the number of participants anticipated in each group.

  Participants will be randomly assigned to either the low-dose Ketamine infusion group or the normal saline infusion group. The two groups will comprise the study population, n=150.
- e. Indicate which, if any, of the special populations listed below will be involved in the protocol. Include the Special Populations Review Form (SPRF) if indicated.

  □ Pregnant Women: Attach SPRF—Pregnant Women, Fetuses, Neonates/Nonviable Neonates

□ Fetuses: Attach SPRF—Pregnant Women, Fetuses, Neonates/Nonviable
Neonates
□ Neonates/Nonviable Neonates: SPRF—Pregnant Women , Fetuses ,
Neonates/Nonviable Neonates
□ Prisoners: Attach SPRF—Prisoners
☐ Minors (<18 years old): Attach SPRF—Minors
⋈ Employees or students at institution where research conducted
☐ Persons who are temporarily decisionally impaired
☐ Persons who are permanently decisionally impaired (e.g., mentally retarded)
□ Non-English Speakers
For each box checked, describe why the group is included and the additional
protections provided to protect the rights and welfare of these participants who
are vulnerable to coercion: Employees and students may be eligible to participate and should
be allowed to do so. It is an undue burden to exclude them. The suggested language has been
included in the informed consent document to fully disclose that this project is separate from the
expectations and their relationship with UAB as an employee or a student.

- **f.** List any persons other than those directly involved in the study who will be at risk. If none, enter "None": None
- g. Describe the process (e.g., recruitment, chart review) that will be used to seek potential participants (e.g., individuals, records, specimens). Research recruitment by non-treating physicians/staff may require completion of Partial Waiver of Authorization for Recruitment/Screening. (See http://main.uab.edu/show.asp?durki=61981.)

  Patients being seen in the pre-operative anesthesia clinic (PAC) that are scheduled for general, ENT, or orthopedic surgery will be screened by the clinician for possible eligibility for this study. Recruitment will take place in the PAC clinic (at the Kirklin Clinic or Highlands PAC clinic) during the PAC clinic visit. Specifically: 1) Study Personnel and Anesthesia providers will be provided a study summary and/or a study outline for reference and guidance. 2) The "Attention Pre-op Clinic" flier will be posted in the PAC clinician's work area as a reminder to the clinicians to screen for potential study patients and as a guide to identify potential study subjects. The flier is for clinician referral. 3) If a patient is identified as a potential study candidate then the PAC clinician or staff will contact (via pager or cell phone) the PI or the study research assistant to inform them of a possible study candidate is in the PAC clinic.
- h. If you will use recruitment materials (e.g., advertisements, flyers, letters) to reach potential participants, attach a copy of each item. If not, identify the source (e.g., databases) from which you will recruit participants.
  See item 15.g.
- Once a potential participant has been identified (see steps outlined in item g above), then the study PI and/or the research assistant will perform a chart review to complete the Eligibility Checklist. If a patient meets the eligibility criteria, as outlined on the Eligibility Checklist, then the PI or the research assistant will meet the patient and present the details of this study to the patient. If the patient agrees to participate, then informed consent will be obtained. Eligibility determination and screening will occur in the Preoperative Assessment Clinic (PAC) in The Kirklin Clinic (TKC) and Highlands.

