#### 6.0 ELIGIBILITY & EXCLUSION CRITERIA

Inclusion criteria: Total of sixty-five patients, aged 19-70, scheduled to undergo laparoscopic gastric bypass surgery for morbid obesity. Patients should have a diagnosis of obstructive sleep apnea as confirmed by sleep study and are not currently using a CPAP devise. If no sleep study is available, patients should have the 4 clinical predictors of obstructive sleep apnea as described by STOP (Snoring, Tiredness during daytime, Observed apnea, high blood Pressure) screening questionnaire. <Chung, F Anesthesiology 2008>

Exclusion criteria: Patients <19 yrs, positive pregnancy test, ASA> III, history of alcohol or narcotic abuse in last 90 days, significant cardiovascular or respiratory disease (baseline oxygen saturation below 92%), significant psychiatric or neurologic disease, history of significant hepatic or renal disease (baseline creatinine>1.5), history of allergy or contraindication to anesthetic agents or ketamine including patients with increased ICP, increased IOP, severe arrhythmias, history of delirium, hallucinations, or psychosis, or history of uncontrolled seizures, or potential risk for malignant hyperthermia (family history), history of difficult intubation that would preclude standard induction of anesthesia, prisoners, persons who are mentally impaired, and non-english speakers.

Criteria for early withdrawal for the study: <2 hrs surgical time, any surgical or anesthetic complication that prevents the assessment of study variables, clinically relevant residual neuromuscular blockade or other reason for patient to require prolonged tracheal intubation following surgery.

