Anesthesia will be maintained in the both groups with inhaled Sevoflurane starting at 4% end-tidal concentration and titrated to keep the bispectral index (BIS) value at 40-50 (Bispectral Index, Aspect Biomedical, Natick, MA). After induction and before surgical incision is made, patients will receive an intravenous bolus saline or the study drug, S(+) ketamine 0.5mg/kg IBW bolus followed by a continuous infusion of 0.5 mg/kg/hr (IBW) using a Baxter syringe pump. The infusion will be stopped at the closure of the abdominal fascia layer, approximately 30 minutes before the end of surgery. In both groups, neuromuscular blockade will be maintained with rocuronium and titrated to train-of-four (TOF) ratio until the abdominal fascia is closed. Oxygen, air (no nitrous oxide), IV fluids, vasoactive drugs, and fentanyl (up to 5mcg/kg IBW) will be titrated at the anesthesiologist's discretion to maintain hemodynamics at 25% of baseline. Glycopyrolate and neostigmine will be given to facilitate reversal of neuromuscular blockade. Sevoflurane will be discontinued immediately prior to completion of surgery. All patients will receive IV ketorolac 30mg at conclusion of closure of abdominal fascia. Endotracheal tube will be removed when patient meets extubation criteria (spontaneous breathing with min 6ml/kg IBW tidal volume, following commands with ability to sustain hand grip and 5-sec head lift). All patients will then be discharged from the operating room to the post-anesthesia care unit (PACU).

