# If study involves drugs or devices skip Items 19.b. and 19.c., go to Item 20, and complete the Drug or Device Review Sheet, as applicable.

- b. If hazards to an individual participant occur, describe (i) the criteria that will be used to decide whether that participant should be removed from the study; (ii) the procedure for removing such participants when necessary to protect their rights and welfare; and (iii) any special procedures, precautions, or follow-up that will be used to ensure the safety of other currently enrolled participants.

  Criteria for early withdrawal for the study: <2 hrs surgical time, any surgical or anesthetic complication that prevents the assessment of study variables, clinically relevant residual neuromuscular blockade or other reason for patient to require prolonged tracheal intubation following surgery.
- c. If hazards occur that might make the risks of participation outweigh the benefits for all participants, describe (i) the criteria that will be used to stop or end the entire study and (ii) any special procedures, precautions, or follow-up that will be used to ensure the safety of currently enrolled participants.

  The overall study will be suspended if is determined that, at any point, study procedures are not adequate to protect the participant's safety. All efforts will be made during procedures to ensure that the participant's risk is minimized.

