#### 23. Additional Information

In the space below, provide any additional information that you believe may help the IRB review the proposed research, or enter "None."

This study was originally closed on May 28, 2014. The PI is now requesting to re-open this protocol. The PI understands that it has been over a year and will have to re-submit the protocol. You will find attached the originally approved HSP. A few personnel were added and removed along with changes to the patient population (now focusing on patients undergoing general ENT or Orthopedic surgery).

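### The re-opened form sets no entry criterion on planned operating time but keeps withdrawal for surgery under 2 hours, so short cases can be randomised and dosed, then expected to be withdrawn

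*Combined protocol and SAP*

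**What the plan says.** The combined document holds the gastric bypass protocol (sections 1.0 to 14.0) and the Human Subjects Protocol form submitted to re-open the study.

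- **Entry, gastric bypass protocol.** Section 6.0 admits patients "scheduled to undergo laparoscopic gastric bypass surgery for morbid obesity", a single operation. The same section withdraws patients whose surgery takes under 2 hours.
- **Entry, re-opened form.** Item 23 announces "changes to the patient population (now focusing on patients undergoing general ENT or Orthopedic surgery"). The criteria in item 15 read "Inclusion criteria: aged 19-100, scheduled to undergo general ENT or Orthopedic Surgery", followed by sleep apnea status. The exclusions are medical, anesthetic and consent-related. Neither list refers to planned or expected operating time.
- **A wider line in the same item.** Under race/ethnicity, item 15.b adds "Expand the patient population to include all patients undergoing surgery requiring to general anesthesia due to the limited amount of patients" who can be recruited.
- **Withdrawal, re-opened form.** Item 19.b states "Criteria for early withdrawal for the study: <2 hrs surgical time, any surgical or anesthetic complication that prevents the assessment of study variables", with the same 2-hour threshold as section 6.0.
- **Order of events.** Eligibility and consent are settled in the preoperative clinic (items 15 and 20). Section 8.0 then says "After induction and before surgical incision is made, patients will receive an intravenous bolus saline or the study drug".
- **Size.** Item 15 gives 150 patients in two groups. Section 11.0 gives 32 per group and 65 in total for the gastric bypass study.

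**The concern.** The 2-hour rule was written for one type of operation. The population was then replaced by a mixed surgical one and the rule stayed as it was. Nothing at screening asks whether the planned operation can be expected to last 2 hours, but the rule takes effect on that quantity after the patient has been consented, allocated and given study drug.

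Three things are at stake. Patients who could have been screened out in the clinic receive an infusion that item 16 classes as research rather than routine care. Recruitment effort goes to patients the plan expects to withdraw, in a study that widened its population because it could not recruit enough. And each such withdrawal happens after randomisation, in a plan that defines no analysis population, no replacement rule and no allowance for short cases.

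**Working it through.** **1. Is the mismatch in the current text?**

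| Step | Where | Depends on operating time? |
|---|---|---|
| Inclusion list | Item 15 | No |
| Exclusion list | Item 15 | No |
| Infusion length | Item 16 procedures table | Upper limit of three hours, no lower limit |
| Study bolus | Section 8.0 | Given before incision |
| Withdrawal | Item 19.b | Yes: under 2 hours |

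Actual operating time is known only when the operation ends. By then the patient has been randomised and dosed. Both halves of the mismatch stand on the same form.

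**2. How many patients?** The documents give no durations, so the share w of operations under 2 hours is an assumption. The number withdrawn is 150 × w:

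- w = 10%: 150 × 0.10 = 15
- w = 20%: 150 × 0.20 = 30
- w = 40%: 150 × 0.40 = 60

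**3. What effect size does the plan's own figure imply?** Section 11.0 gives 32 per group, 80% power, 5% type 1 error and a decrease of more than 30% in opioid requirement. It gives no mean, SD or sidedness, so 32 cannot be reproduced, only solved backwards. For a two-sided test (assumed):

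d = (1.960 + 0.842) × √(2/32) = 0.70 (0.71 by the t-test).

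For a 30% decrease this means an SD of 0.30/0.70 = 43% of the control mean (42% by the t-test).

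**4. Does the loss threaten that power at 150?** Take the worst case, in which every withdrawn patient is left out of the analysis. With n per group = 150(1 − w)/2, power = Φ(d√(n/2) − 1.960):

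| w | n per group | d√(n/2) − 1.960 | Power, normal | Power, t-test |
|---|---|---|---|---|
| 0 | 75 | 2.33 | 0.990 | 0.991 |
| 10% | 67.5 | 2.11 | 0.983 | 0.984 |
| 20% | 60 | 1.88 | 0.970 | 0.972 |
| 40% | 45 | 1.36 | 0.913 | 0.916 |

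The 64 evaluable patients of section 11.0 remain until w = 1 − 64/150 = 57.3%.

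If the 5% was one-sided, the implied d is 0.62. At w = 40%, 0.6216 × √(45/2) − 1.645 = 1.30, which is still about 90% power.

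**5. Limit of this check.** It carries the gastric bypass effect size over to a mixed surgical population, and the documents give no basis for a different one. With an assumed SD of 60% of the control mean, the same formula needs 63 per group, or 126 in all. In that case 150 tolerates only 24/150 = 16% withdrawn.

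**The case against.** The strongest reply accepts the wording but disputes how much follows from it.

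- **Booked time is not actual time.** A reader might infer that a patient booked for a short operation is certain to be withdrawn and lost. The documents do not support that. Operations overrun, surgical time is not defined, and nowhere is a withdrawn patient said to be left out of the analysis or the safety data. *Expected to be withdrawn* is as far as the text goes. This part stands.
- **Power.** A reader might apply a mixed case load to the 65 patients of section 11.0 and find power falling to about 76%, 71% or 58% at 10%, 20% or 40% withdrawn. But 65 belongs to the single-procedure gastric bypass study, and the wider population comes with 150. That pairing describes neither plan. This part stands.
- **The frequency is unknown and may be small.** True. It limits any statement of size, but not the finding that the two items do not fit together.
- **The Eligibility Checklist is not reproduced and may screen on duration.** It may. The criteria it is meant to implement do not.
- **The form tells drug studies to skip item 19.b, and section 13.0 lists removal criteria without the 2-hour rule.** Item 19.b was completed all the same, and section 6.0 carries the same rule. These points add to the need for reconciliation and do not remove it.
- **The 2-hour rule could be dropped instead.** This is a fair alternative. The documents do not settle which item should give way.

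**Conclusion.** The concern holds as a mismatch between entry and withdrawal on the re-opened form. Followed as written, the plan can randomise and dose patients whose booked operation cannot be expected to satisfy its own 2-hour rule.

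Under assumed shares of 10%, 20% or 40% short operations, 15, 30 or 60 of 150 patients would be withdrawn after randomisation. The true share is not in the documents. The stated power is not the casualty: at the effect size implied by 32 per group it stays above 90% across that range with 150 enrolled, even if every withdrawn patient is left out of the analysis. That rests on a two-sided 5% test and on the gastric bypass effect size applying to the new population. The cost lies in avoidable exposure, wasted recruitment and withdrawals after randomisation.

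Section 6.0 covers a single procedure and does not need changing on this ground. The line extending entry to all surgery under general anesthesia appears only in item 15.b. The formal criteria still name general ENT or orthopedic surgery, and the mismatch exists under either reading.

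**What to change.** Reconcile items 15 and 19.b, in one of two ways, for the investigators to choose:

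1. **If the 2-hour withdrawal rule is kept,** add to item 15 and to the Eligibility Checklist that the scheduled operative time must be at least 2 hours, read at the clinic visit.
2. **If the rule is no longer wanted for the wider population,** remove it from item 19.b so that short cases stay in the study.

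The first option costs one line in the criteria and one on the checklist. It shrinks the recruitment pool, though mostly by patients who would be withdrawn anyway. It does not catch everything: some operations booked for 2 hours or more will finish early and still be withdrawn after dosing. It also assumes that planned duration can be read at the clinic visit, which the documents do not say. The second option costs a deletion and keeps the pool intact.

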# 11.0 STATISTICAL CONSIDERATIONS

Statistical analysis with *a priori* power analysis was performed to determine the number of patients per group sufficient to detect a decrease of >30% in postoperative opioid requirements on the basis of the results of Kararmaz et al., Anesthesia and Analgesia 2003. With a power of 80% and a type 1 error of 5%, it was estimated that 32 patients will be required per group. We will plan to enroll 65 patients total to account for unanticipated subject dropout. Mann-Whitney U-test will be used to compare VRS, modified Aldrete, and patient satisfaction scores. Student's t-test will be used to compare BMI, time to first analgesic, number of analgesic demands, amount of analgesic consumption and ODI. The X2 test will be used to compare frequency of side effects, race and sex distribution. The resulting values will be expressed as mean +/- SD or median and range with P< 0.05 considered statistically significant.

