# 16. Protocol Procedures, Methods, and Duration of the Study—in nontechnical language

- Participants in this study will be randomized to two groups: One group will receive an intravenous (IV) dose of ketamine during the surgery. The other group will receive a normal saline placebo IV (control group). For the patients that are randomized to the ketamine group, the PI will submit an order for the ketamine to the research pharmacist. The pharmacist will determine the dosing of ketamine based on a standard calculation and prepare the syringe that will be used to dispense the ketamine. For both groups, the IV infusion will be discontinued at the conclusion of the surgery. Participants will receive standard anesthetic drugs and appropriate pain medication to control their postoperative pain in keeping with the current practice. We will compare recovery data including vital signs and pain scores as well as potential side effects of controlled versus study group. Approximately 24 hours after surgery, a patient assessment form will be completed ("24 Hr Post-Operative Data Collection Form") by the PI or research study team.
- b. What is the probable length of time required for the entire study (i.e., recruitment through data analysis to study closure)?
  Approximately two years
- Participants will be involved during surgery, during their recovery in the PACU, and at one time point approximately 24 hours postoperatively (to complete the Post-Operative Patient Satisfaction Assessment Form).
- d. If different phases are involved, what is the duration of each phase in which the participants will be involved? If no phases are involved, enter "not applicable." Not applicable
- **e.** List the procedures, the length of time each will take, and the frequency of repetition, and indicate whether each is done solely for research or would already be performed for treatment or diagnostic purposes (routine care) for the population. *Insert additional table rows as needed.*

Procedure	Length of Time	Frequency of	Doscorrah (Dos)
rioccarc			Research (Res) -
	Required of	Repetition	OR- Routine Care
	Participants		
Pregnancy testing for women of	<5 minutes	once	□Res ⊠Routine
childbearing potential			
Weight measurement	<5 minutes	once	□Res ⊠Routine
Normal Saline or Ketamine infusion	<three hours<="" td="">once	⊠Res □Routine	</three>	once	⊠Res □Routine
Monitoring and measurement of	From onset of	Continuously	□Res ⊠Routine

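### Prescribed daily opioid use and a planned regional block are neither screened for nor listed as baseline data, so the unadjusted test of opioid consumption gives up precision that two covariates would recover

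*Combined protocol and SAP*

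**What the plan says.** **Powered outcome.** Protocol sections 5.0 and 11.0 size the trial on one outcome, with a number of patients "sufficient to detect a decrease of >30% in postoperative opioid requirements". "With a power of 80% and a type 1 error of 5%, it was estimated that 32 patients will be required per group". Section 11.0 then assigns analgesic consumption to Student's t-test and names no covariate.

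**Eligibility.** The exclusion lists in protocol section 6.0 and Human Subjects Protocol item 15 both deal with opioid exposure only as "history of alcohol or narcotic abuse in last 90 days". Neither mentions prescribed use, and neither mentions regional anesthesia.

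**Perioperative analgesia.** Protocol section 9.0 declares concomitant therapies not applicable. Item 16 promises "appropriate pain medication to control their postoperative pain in keeping with the current practice". The background, in general terms, says "opioids should be avoided in favor of nonsedating agents such as acetaminophen, ketorolac or even regional anesthesia when possible".

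**Data.** Protocol section 8.0 lists demographics, time to first analgesic, analgesic demands, analgesic consumed in the OR and PACU, side effects and desaturation index, and adds a 24-hour assessment. Preoperative opioid use and block use are not on the list. Allocation is by closed envelope, with no stratification described.

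**Population and size.** The protocol enrolls laparoscopic gastric bypass patients: "We will plan to enroll 65 patients total to account for unanticipated subject dropout". The Human Subjects Protocol moves to general, ENT or orthopedic surgery (items 15 and 23), and one line of item 15 extends this to any surgery under general anesthesia. There, "The two groups will comprise the study population, n=150", with no power statement.

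**The concern.** Both factors plausibly predict how much opioid a patient needs after surgery: daily users more, patients with a working block less. If both kinds of patient enter, the outcome varies more between patients than in a uniform population. An unadjusted t-test puts all of that variation into its error term. A chance imbalance in either factor would move the estimated difference, and without a baseline record nobody could show the imbalance or correct for it. At stake is the precision of the one comparison for which the trial was sized.

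**Working it through.** **Inputs from the documents.** 30% relative reduction, 80% power, 5% type 1 error, 32 per group (section 11.0); n=150 in two groups (item 15), which is 75 per group if allocation is 1:1 (the ratio is not stated).

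**Not in the documents, so assumed.** Mean and SD of opioid requirement, sidedness of the test, the share p of patients with each factor, and the multiplier k on their requirement.

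**Step 1: the plan's 32.** It cannot be reproduced without a mean and SD, only solved backwards. With d = 0.30 × mean / SD, a two-sided t-test with 32 per group has 80% power at d = 0.711, so SD/mean = 0.30/0.711 = 0.42. The normal approximation gives d = (1.960 + 0.842) × √(2/32) = 0.700 and SD/mean = 0.43. A one-sided test would imply about 0.48. I use two-sided 0.42.

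**Step 2: mixed population.** Give patients with neither factor a control mean of 100 and SD of 42.17 (variance 1778). A share p has mean and SD multiplied by k. Ketamine lowers every mean by 30%, and both arms take the control SD.

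- Mean: M = 100 × (1 − p + pk)
- Variance within strata: W = 1778 × (1 − p + pk²)
- Variance between strata: B = p(1 − p) × [100(k − 1)]²
- Unadjusted: d = 0.30M / √(W + B)

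Example, p = 0.2 and k = 2: M = 120; W = 1778 × 1.6 = 2845; B = 0.16 × 10,000 = 1600; SD = √4445 = 66.7; d = 36/66.7 = 0.540.

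**Step 3: adjusted analysis.** A covariate for the factor removes B, so d = 0.30M / √W. In the example, 36/53.3 = 0.675. The small loss of degrees of freedom is ignored.

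Power by noncentral t, two-sided 5%:

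| Scenario | M | W | B | d unadjusted | Power 32 / 75 per group | d adjusted | Power 32 / 75 per group |
|---|---|---|---|---|---|---|---|
| 20% daily users, k = 1.5 | 110 | 2222 | 400 | 0.644 | 72% / 97.5% | 0.700 | 79% / 99% |
| 20% daily users, k = 2 | 120 | 2845 | 1600 | 0.540 | 57% / 91% | 0.675 | 76% / 98% |
| 20% blocked, k = 0.2 | 84 | 1437 | 1024 | 0.508 | 52% / 87% | 0.665 | 74% / 98% |
| 30% blocked, k = 0.2 | 76 | 1266 | 1344 | 0.446 | 42% / 77% | 0.641 | 71% / 97% |
| 20% users (k = 2) plus 20% blocked (k = 0.2) | 104 | 2503 | 3264 | 0.411 | 37% / 71% | 0.624 | 69% / 97% |

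**Step 4: chance imbalance.** For a factor with 20% prevalence, two independent binomial counts differ by at least 10 percentage points with probability 27% at 32 per group and 13% at 75 per group. With k = 2, a 10-point imbalance moves the difference in means by 0.10 × 100 = 10 units, against a true difference of 0.30 × 120 = 36 (28% of it). With k = 0.2 it moves it by 0.10 × 80 = 8 units, against 0.30 × 84 = 25.2 (32% of it).

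**The case against.** **The low power figures do not describe the current population.** The 32 per group belongs to the gastric bypass protocol, whereas the widened population comes with n=150. At 75 per group every single-factor scenario at 20% stays above the planned 80%. This stands, so the point is not that the current trial is underpowered. What remains is that the 150 carries no power calculation, so the documents do not show that it allows for this variation, and the two harsher scenarios fall to 77% and 71%.

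**A reader might infer that such patients bias the comparison or dilute the 30% contrast.** Neither follows. Randomisation makes the two arms alike on average. With the same proportional effect in everyone, the contrast stays at exactly 30% while the spread rises; for daily users the absolute difference even grows, from 30 to 36 units at k = 2. The t-test's type 1 error over repeated randomisations already allows for chance imbalance. What is lost is precision, and the means to examine the allocation that actually occurred.

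**No block is planned.** Protocol section 8.0 specifies general anesthesia with intravenous analgesics, and item 18 gives local standard care as a balanced general anesthetic with intravenous opioids afterwards. The background sentence on regional anesthesia is general commentary, and the next one expects most patients to need intravenous opioids after major surgery. This weakens the block half of the point: a block is not barred, but the documents do not say that blocks will be used. The daily-opioid half does not depend on it.

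**A reader might infer that neither factor is recorded.** That cannot be shown. The Eligibility Checklist and the 24-hour forms are named but not reproduced. The supportable statement is that the documents list no such item.

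**The starting SD is arbitrary.** It is back-solved, and the source of the sizing is, by its title in the reference list, a renal-surgery study of ketamine added to epidural analgesia. This stands: every power figure above is illustrative.

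**Conclusion.** The point holds as one of precision. The criteria admit patients on prescribed daily opioids and do not bar a planned block, the documents list no collection of either, and the powered outcome is tested without adjustment. With 20% of patients carrying one factor, unadjusted power is about 52% to 72% at 32 per group and 87% to 97.5% at 75 per group. Across the four single-factor scenarios in the table, adjustment brings it to about 71% to 79% and 97% to 99%. These figures rest on an implied SD/mean of 0.42, 1:1 allocation for the 75, an equal proportional effect in all patients, and shares and multipliers that the documents do not give.

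It may be tempting to conclude that both kinds of patient must be excluded. The documents do not require that. Item 15 says that the population was widened because too few patients could be recruited, so exclusion is a trade-off. Adjustment is a cheap improvement, worth making whatever the investigators decide on eligibility.

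**What to change.** 1. Add two fields to the chart review and Eligibility Checklist described in Human Subjects Protocol item 15, completed before randomisation: daily preoperative opioid use over a fixed look-back period (yes/no, with daily morphine equivalent), and planned regional block (yes/no). Record the plan, not only what was done, because a block chosen after study drug has started could depend on treatment.
2. In protocol section 11.0, replace the unadjusted t-test of opioid consumption with a prespecified linear model containing treatment and both covariates, reporting the adjusted difference with its confidence interval. Report both factors by arm at baseline.

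The cost is two baseline fields, taken from a chart review that already happens, and one covariate model. No change to eligibility or care is needed. Whether such patients should be excluded is left to the investigators.
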